8.6.6. Physical Examination

Patient listings of whether physical examination was performed or not will be presented for the Safety Analysis Set.

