3.6.2.5 Physical Examination

The physical examination will include general appearance, skin, neck (including thyroid), eyes, ears, nose, throat, heart, lungs, abdomen, lymph nodes, extremities, and nervous system. Clinically significant changes from screening/baseline in the physical examination for a surgical or medical patient will not be recorded as AEs unless they are of greater severity and/or intensity than would be expected.

Trevena, Inc.

Protocol CP130-3003

Version 5.0

14 Sep 2016

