4.1 Definitions and Criteria

4.1.1 Adverse Events

An AE is any untoward medical occurrence in a study patient that is temporally associated with the use of a medicinal product, regardless of its potential relationship to the medicinal product. An AE, therefore, can be any unfavorable or unintended sign, including a clinically significant abnormal laboratory finding, symptom, or disease temporally associated with the use of the IP, whether or not it is considered to be IP related. This includes any newly occurring event or previous condition that has increased in severity or frequency from time of informed consent.

Examples of an AE include:

- Exacerbation of a pre-existing condition, including either an increase in frequency and/or intensity of the condition.
- A new condition detected or diagnosed.
- Signs or symptoms of a drug interaction.
- Signs or symptoms of a suspected overdose of either IP or a concurrent medication (overdose per se should not be reported as an AE/SAE).
- A new laboratory abnormality that results in patient withdrawal from the study or medical treatment or further follow-up.

NOTE: abnormal laboratory values obtained during screening that preclude a patient from entering the study are not considered AEs, but they will be recorded.

AEs may include pre- or post-treatment events that occur as a result of protocol-mandated procedures (ie, invasive procedures, modification of patient's previous therapeutic regimen).

Symptoms or signs anticipated for a surgical or medical patient will not be recorded as AEs unless they are of greater severity and/or intensity than would be expected. Investigators will use

Trevena, Inc.

Protocol CP130-3003

Version 5.0

14 Sep 2016

their clinical judgment in determining whether the symptoms or signs are of greater severity and/or intensity than would be expected.

A medical intervention to address an AE is an “action taken” and not an AE in itself.

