6.3 Safety and Tolerability Analyses

The number and incidence of AEs/SAEs will be summarized overall and by severity and causality. MedDRA Version 19.0 will be used to classify all events with respect to system organ class and preferred term. WHODD (March 2016) will be used to categorize prior and concomitant medications. Summaries will include only treatment-emergent AEs (TEAEs) and will be summarized for the safety and tolerability analysis data set. Clinically significant changes in vital sign measurements, oxygen saturation measurements, somnolence/sedation scores, physical examination findings, and clinical laboratory assessments will be summarized via descriptive summary statistics.

Summary statistics for observed values and change from baseline values for vital sign measurements, oxygen saturation measurements, somnolence/sedation scores, physical examination findings, and clinical laboratory assessments will be summarized. Baseline values are defined as the last measurements taken before the first dose of oliceridine. SOWS total scores will be summarized.

Prior and concomitant medications will be summarized.

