6.3.6 Physical Examination

The physical examination will include general appearance. Results from screening/baseline will be recorded as medical history events while changes from screening/baseline in the physical examination will be recorded as AEs. The investigator will exercise his or her medical and scientific judgment in deciding whether an abnormal finding is clinically significant.

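### The SAP drops the protocol's summary of physical-examination changes without declaring it, and its rule that changes become AEs conflicts with the protocol's exception for surgical and medical patients

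*SAP*

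**What the plan says.** Protocol 6.3 names physical-examination findings in two planned analyses. The first covers clinically significant changes in five kinds of assessment: "Clinically significant changes in vital sign measurements, oxygen saturation measurements, somnolence/sedation scores, physical examination findings, and clinical laboratory assessments will be summarized". The second covers observed and change-from-baseline values: "Summary statistics for observed values and change from baseline values for vital sign measurements, oxygen saturation measurements, somnolence/sedation scores, physical examination findings", followed by laboratory results. The synopsis repeats both.

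SAP 8.6.6 consists of one sentence: "Patient listings of whether physical examination was performed or not will be presented for the Safety Analysis Set". In the mock displays the only examination output is Listing 16.2.10, whose columns are the patient identifier, the assessment date and time, and whether anything changed since the previous visit.

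On how examination changes enter the AE data, SAP 6.3.6 says "changes from screening/baseline in the physical examination will be recorded as AEs", with no exception. Protocol 3.6.2.5 says that clinically significant changes "in the physical examination for a surgical or medical patient will not be recorded as AEs unless they are of greater severity" or intensity than would be expected. Protocol 4.1.1 applies the same exception to symptoms and signs in general: "Symptoms or signs anticipated for a surgical or medical patient will not be recorded as AEs unless they are of greater severity and/or intensity" than expected.

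Protocol section 6 requires the SAP and the clinical study report to describe any change from the protocol's analyses. SAP section 5 only refers the reader to the protocol amendments.

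**The concern.** Safety is the primary objective, and the study is open-label with no comparator. Whether a postoperative or disease-related change is expected is therefore an unblinded investigator's judgement. A table of examination changes that does not depend on AE classification would let a reader see how much was set aside under that judgement. The protocol planned such a summary and the SAP does not deliver it.

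Reading SAP 6.3.6 alone, one would suppose that the AE tables cover the loss. Under the protocol's exception they cover only part of it.

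**Working it through.** No arithmetic applies: the study is descriptive and neither document gives a figure on this point. The check is a comparison of texts.

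1. **Promised against planned.** The first Protocol 6.3 sentence names vital signs, oxygen saturation, sedation scores, physical-examination findings and laboratory results. In the SAP's mock displays, vital signs have Tables 14.3.5.1 and 14.3.5.1.1, oxygen saturation has Table 14.3.5.2 and a row in 14.3.5.1.1, sedation has Table 14.3.6.1, and laboratory results have the 14.3.3 series and Table 14.3.4.1. Physical examination has no table. It is the only one of the five with no summary output.

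2. **SAP text against shell.** SAP 8.6.6 describes a listing of whether the examination was done. The shell for Listing 16.2.10 has a column for change since the previous visit, so the two disagree and the shell shows more. The shell has no grade of clinical significance, whereas the laboratory and ECG shells separate clinically significant from not clinically significant abnormalities. It does not label the change as from screening or baseline, and it has no link to an AE record.

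3. **Route into the AE tables.**

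| Examination change, surgical or medical patient | SAP 6.3.6 | Protocol 3.6.2.5 |
|---|---|---|
| Clinically significant, worse than expected | AE | Not exempt; can be an AE |
| Clinically significant, as expected | AE | Not an AE |

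Sites record AEs under the protocol, so the second row does not reach the AE tables in SAP 8.6.3. By step 1 it reaches no examination table either. Its only trace is the per-patient listing. The exception does not name ED patients.

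4. **Declaration.** SAP section 5 does not mention the dropped summary. Its pointer to the amendments does not cure this, because Protocol Version 5.0, the version under review, still contains the summary in section 6.3.

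**The case against.** Several points on the other side are sound, and they rule out stronger readings that a reader might infer.

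- **Lost endpoint data.** Protocol 1.3.1 measures safety as the incidence of AEs, including AEs related to examination findings. A change that the protocol deliberately does not count as an AE is outside that measure. What is lost is a supportive summary.
- **Changes invisible in the report.** The shell of Listing 16.2.10 has a column for them. They are listed but not tabulated.
- **All surgical and medical patients affected.** Only those with a clinically significant change judged expected fall into the gap. Worse-than-expected changes are not exempt and remain eligible for the AE tables.
- **Summary dropped because of SAP 6.3.6.** SAP 8.6.6 gives no reason, and no text links the two sections. Only the conflict between SAP 6.3.6 and Protocol 3.6.2.5 is established.
- **The missing table already exists in the data.** For the reasons in step 2, the listing's change column alone does not supply clinical significance or AE matching.

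It can also be argued that Protocol 4.1.3 makes clinically significant abnormal assessments reportable as AEs. That rule is general, gives vital signs as its example, and applies to findings that meet the AE definition. Protocol 3.6.2.5 is specific to the examination. At most this is a further passage to reconcile.

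Finally, without a comparator, expected postoperative changes say little about oliceridine. That limits what the table can show, but it does not excuse an undeclared departure from a planned safety analysis.

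**Conclusion.** The point holds in this limited form. One summary promised in Protocol 6.3 is missing from the SAP and its displays, the departure is undeclared, and SAP 6.3.6 contradicts Protocol 3.6.2.5. Together these leave clinically significant changes judged expected, in surgical or medical patients, outside every summary table.

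The size is unknown. The documents give neither the share of surgical and medical patients among the roughly 1000 to be treated nor any rate of examination change. The conclusion assumes that sites follow the protocol's AE rule and that the mock displays are the complete set of planned outputs. It does not put the study's validity in doubt, but it should be corrected before the database is locked.

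**What to change.** 1. Reconcile SAP 6.3.6 with Protocol 3.6.2.5, so that the SAP states which examination changes enter the AE data.
2. In SAP 8.6.6, add one count-and-percentage table for the Safety Analysis Set, by cumulative dose group, overall and by initial setting. Rows: patients examined at end of treatment; patients with a recorded change; and, where the eCRF and AE records allow, those changes split by clinical significance and by whether a matching AE was reported. Bring the 8.6.6 text into line with the Listing 16.2.10 shell.
3. In SAP section 5, state any part of the Protocol 6.3 summary that cannot be produced, and why. If the eCRF holds no grade of clinical significance, say so there.

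The cost is one extra table, the wording changes, and some cross-checking of examination records against AE records. Many tabulated changes will reflect the surgery or the underlying condition rather than the drug, and a footnote should say so.

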8.6.7. ECG

Continuous descriptive summaries (n, mean, SD, median, minimum, and maximum) of actual values and changes from baseline will be calculated for HR, PR interval, RR interval, QRS interval, QT interval, and QTcF interval for the Safety Analysis Set. These summaries will be provided by time point in accordance with the windowing defined in Section 6.2.4.

The number and percentage of patients with normal and abnormal ECG results will be displayed by each cumulative dose group and for all groups combined.

In addition, a listing of electrocardiogram results will be presented for each patient.

8.6.8. Subjective Opiate Withdrawal Scale (SOWS)

SOWS total score will be summarized with descriptive statistics (number of patients [N], mean, standard deviation [SD], median, minimum, and maximum) for the Safety Analysis Set. All SOWS results will also be listed by treatment.

8.6.9. Pharmacokinetic Procedures

Plasma concentration values (scheduled and unscheduled) will be summarized for the Safety Analysis Set over time using descriptive summary statistics and the analysis windows described in section 6.2.4. All plasma concentration values will be listed at each time point where an assessment has occurred.

Client: Trevena, Inc.
 Version #: 1.0
 Version Date: 20Dec2016

Protocol/CIP #: CP130-3003

8.7 Analysis of Efficacy Parameters

The Efficacy Analysis Set will be the population for all efficacy variables. Descriptive summary statistics will be tabulated by time interval, by cumulative dose group and for all groups combined. No formal statistical testing will be performed on the efficacy endpoints.

8.7.1. Analysis of NPRS

Continuous descriptive summaries (n, mean, SD, median, minimum, and maximum) of actual values and changes from baseline will be calculated for the NPRS values for the Efficacy Analysis Set. All NPRS assessments will be listed for each actual time point where an assessment has occurred.

8.7.2. Exploratory Analyses

No exploratory analyses of efficacy data are planned.

9. Computer Software

All analyses will be performed by Chiltern, International, using Version 9.3 or later of SAS® software. All summary tables, figures and data listings will be prepared utilizing SAS® software.

11. APPENDICES

11.1 APPENDIX 1: VARIABLE DEFINITIONS

Age will be calculated as the informed consent date minus the date of birth divided by 365.25 [Age=(ICF Date-DOB)/365.25].

Body mass index (BMI; kg/m²) is calculated as: weight (kg) / [height (m)]², rounded to one decimal place.

Chiltern, International – Confidential

Client: Trevena, Inc.
Version #: 1.0
Version Date: 20Dec2016

Protocol/CIP #: CP130-3003

Height and weight are collected in imperial units and will be converted using the following conversion factors:

Height (cm) = height (inches) x 2.54

Weight (kg) = weight (lb) x 0.454

Temperature is collected in degrees Fahrenheit and will be converted to degrees Celcius using the following formula:

$$\text{Temp } (\text{°C}) = [\text{temp } (\text{°F}) - 32] \times \frac{5}{9}$$

Protocol Number CP130-3003

A phase 3, multicenter, open-label study to evaluate the safety of oliceridine (TRV130) in patients with acute pain for which parenteral opioid therapy is warranted

**Mock Data Displays
Final Version 1.0
Date: 20Dec 2016**

Prepared for:
Trevena, Inc.
[name]
[name]

Prepared by:
Chiltern International, Inc.
[name]
[name]

This document is confidential information of Trevena. It may not be disclosed to parties not associated with the clinical investigation or used for any purpose without the prior written consent of Trevena.

Trevena, Inc.
 Protocol CP130-3003
 Mock Data Displays

Table 14.1.1 Protocol Deviation (Safety Analysis Set)	6
Table 14.1.2.1 Patient Population (Enrolled Analysis Set).....	8
Table 14.1.2.2 Summary of Safety Analysis Set (Safety Analysis Set).....	9
Table 14.1.2.3 Summary of Reasons for Screen Failure (Enrolled Analysis Set).....	10
Table 14.1.3 Summary of Reasons for Receiving Oliceridine (Safety Analysis Set).....	11
Table 14.1.4 Medical History by Body System and Medical Condition (Safety Analysis Set)	12
Table 14.1.5 Summary of Patient Disposition (Safety Analysis Set)	13
Table 14.1.6 Demographic and Baseline Characteristics (Safety Analysis Set).....	14
Table 14.1.7 Summary of Prior Medications by Drug Class and Medication (Safety Analysis Set)	18
Table 14.1.8 Summary of Concomitant Medications by Drug Class and Medication (Safety Analysis Set).....	19
Table 14.2.1 Summary of Numeric Pain Rating Scale Change From Baseline (Efficacy Analysis Set)....	20
Table 14.3.1.1 Exposure to Study Drug (Safety Analysis Set).....	21

Listing 16.2.12.x Patient Profiles for Patients with Durations over 96 Hours (Safety Analysis Set)	73
Figure 1.1 Duration of Treatment by Site (Safety Analysis Set)	75
Figure 1.2 Cumulative Dose by Site (Safety Analysis Set)	76
Figure 2.1 Cumulative Dose by Duration of Treatment (Safety Analysis Set)	77
Figure 2.1.1 Cumulative Dose by Duration of Treatment for Patients With at Least 1 TEAE (Safety Analysis Set)	78

Trevena, Inc.
Protocol CP130-3003
Mock Data Displays

Figure 2.1.2 Cumulative Dose by Duration of Treatment for Patients With at Least 1 Related TEAE (Safety Analysis Set)..... 78

Figure 2.1.3 Cumulative Dose by Duration of Treatment for Patients With at Least 1 TEAE Leading to Discontinuation (Safety Analysis Set)..... 78

Figure 2.1.4 Cumulative Dose by Duration of Treatment for Patients With at Least 1 SAE (Safety Analysis Set)..... 78

Table 14.1.1
Protocol Deviations
(Safety Analysis Set)

Protocol Deviation	Oliceridine <= 4 mg N=XXX n (%) [E]	Oliceridine >4 to 8 mg N=XXX n (%) [E]	Oliceridine >8 to 16 mg N=XXX n (%) [E]	Oliceridine >16 to 36 mg N=XXX n (%) [E]	Oliceridine >36 mg N=XXX n (%) [E]	All Treated Patients N=XXX n (%) [E]
Number of Patients with a Protocol Deviation	xxx (xxx.x) [E]	xxx (xxx.x) [E]	xxx (xxx.x) [E]	xxx (xxx.x) [E]	xxx (xxx.x) [E]	xxx (xxx.x) [E]
Minor	xxx (xxx.x) [E]	xxx (xxx.x) [E]	xxx (xxx.x) [E]	xxx (xxx.x) [E]	xxx (xxx.x) [E]	xxx (xxx.x) [E]
Major	xxx (xxx.x) [E]	xxx (xxx.x) [E]	xxx (xxx.x) [E]	xxx (xxx.x) [E]	xxx (xxx.x) [E]	xxx (xxx.x) [E]
Procedure Window	xxx (xxx.x) [E]	xxx (xxx.x) [E]	xxx (xxx.x) [E]	xxx (xxx.x) [E]	xxx (xxx.x) [E]	xxx (xxx.x) [E]
Minor	xxx (xxx.x) [E]	xxx (xxx.x) [E]	xxx (xxx.x) [E]	xxx (xxx.x) [E]	xxx (xxx.x) [E]	xxx (xxx.x) [E]
Major	xxx (xxx.x) [E]	xxx (xxx.x) [E]	xxx (xxx.x) [E]	xxx (xxx.x) [E]	xxx (xxx.x) [E]	xxx (xxx.x) [E]
Inclusion/Exclusion Criteria	xxx (xxx.x) [E]	xxx (xxx.x) [E]	xxx (xxx.x) [E]	xxx (xxx.x) [E]	xxx (xxx.x) [E]	xxx (xxx.x) [E]
Minor	xxx (xxx.x) [E]	xxx (xxx.x) [E]	xxx (xxx.x) [E]	xxx (xxx.x) [E]	xxx (xxx.x) [E]	xxx (xxx.x) [E]
Major	xxx (xxx.x) [E]	xxx (xxx.x) [E]	xxx (xxx.x) [E]	xxx (xxx.x) [E]	xxx (xxx.x) [E]	xxx (xxx.x) [E]
Unapproved Medication	xxx (xxx.x) [E]	xxx (xxx.x) [E]	xxx (xxx.x) [E]	xxx (xxx.x) [E]	xxx (xxx.x) [E]	xxx (xxx.x) [E]
Minor	xxx (xxx.x) [E]	xxx (xxx.x) [E]	xxx (xxx.x) [E]	xxx (xxx.x) [E]	xxx (xxx.x) [E]	xxx (xxx.x) [E]
Major	xxx (xxx.x) [E]	xxx (xxx.x) [E]	xxx (xxx.x) [E]	xxx (xxx.x) [E]	xxx (xxx.x) [E]	xxx (xxx.x) [E]
Missed Procedure	xxx (xxx.x) [E]	xxx (xxx.x) [E]	xxx (xxx.x) [E]	xxx (xxx.x) [E]	xxx (xxx.x) [E]	xxx (xxx.x) [E]
Minor	xxx (xxx.x) [E]	xxx (xxx.x) [E]	xxx (xxx.x) [E]	xxx (xxx.x) [E]	xxx (xxx.x) [E]	xxx (xxx.x) [E]
Major	xxx (xxx.x) [E]	xxx (xxx.x) [E]	xxx (xxx.x) [E]	xxx (xxx.x) [E]	xxx (xxx.x) [E]	xxx (xxx.x) [E]

Note: E = Number of deviation events.

Percentages are based on the number of patients in each cumulative dose group.

Trevena, Inc.
Protocol CP130-3003CONFIDENTIAL
Page x of yTable 14.1.1 (Continued)
Protocol Deviations
(Safety Analysis Set)

Protocol Deviation Deviation Criticality	Oliceridine <= 4 mg N=XXX n (%) [E]	Oliceridine >4 to 8 mg N=XXX n (%) [E]	Oliceridine >8 to 16 mg N=XXX n (%) [E]	Oliceridine >16 to 36 mg N=XXX n (%) [E]	Oliceridine >36 mg N=XXX n (%) [E]	All Treated Patients N=XXX n (%) [E]
Informed Consent	xxx (xxx.x) [E]	xxx (xxx.x) [E]	xxx (xxx.x) [E]	xxx (xxx.x) [E]	xxx (xxx.x) [E]	xxx (xxx.x) [E]
Minor	xxx (xxx.x) [E]	xxx (xxx.x) [E]	xxx (xxx.x) [E]	xxx (xxx.x) [E]	xxx (xxx.x) [E]	xxx (xxx.x) [E]
Major	xxx (xxx.x) [E]	xxx (xxx.x) [E]	xxx (xxx.x) [E]	xxx (xxx.x) [E]	xxx (xxx.x) [E]	xxx (xxx.x) [E]
Incorrectly Performed Procedure	xxx (xxx.x) [E]	xxx (xxx.x) [E]	xxx (xxx.x) [E]	xxx (xxx.x) [E]	xxx (xxx.x) [E]	xxx (xxx.x) [E]
Minor	xxx (xxx.x) [E]	xxx (xxx.x) [E]	xxx (xxx.x) [E]	xxx (xxx.x) [E]	xxx (xxx.x) [E]	xxx (xxx.x) [E]
Major	xxx (xxx.x) [E]	xxx (xxx.x) [E]	xxx (xxx.x) [E]	xxx (xxx.x) [E]	xxx (xxx.x) [E]	xxx (xxx.x) [E]

Note: E = Number of deviation events.

Percentages are based on the number of patients in each cumulative dose group.

Table 14.1.2.1
Patient Populations
(Enrolled Analysis Set)

Population	All Enrolled Patients N=XXX n(%)
Enrolled Analysis Set	xxx (xxx.x)
Safety Analysis Set	xxx (xxx.x)
Efficacy Analysis Set	xxx (xxx.x)

Note: Percentages based on the total number of enrolled patients.

Table 14.1.2.2
Summary of Safety Analysis Set
(Safety Analysis Set)

Population Site Number	Oliceridine <= 4 mg N=XXX n (%)	Oliceridine >4 to 8 mg N=XXX n (%)	Oliceridine >8 to 16 mg N=XXX n (%)	Oliceridine >16 to 36 mg N=XXX n (%)	Oliceridine >36 mg N=XXX n (%)	All Treated Patients N=XXX n (%)
Safety Analysis Set	xxx (xxx.x)	xxx (xxx.x)	xxx (xxx.x)	xxx (xxx.x)	xxx (xxx.x)	xxx (xxx.x)
Site 1	xxx (xxx.x)	xxx (xxx.x)	xxx (xxx.x)	xxx (xxx.x)	xxx (xxx.x)	xxx (xxx.x)
Site 2	xxx (xxx.x)	xxx (xxx.x)	xxx (xxx.x)	xxx (xxx.x)	xxx (xxx.x)	xxx (xxx.x)
...						

Note: Percentages are based on the number of patients in each cumulative dose group.

Table 14.1.2.3
Summary of Reasons for Screen Failure
(Enrolled Analysis Set)

Parameter	All Enrolled Patients N=XXX n (%)
Number of Screen Failure Patients	xxx (xxx.x)
Number of Patients with Inclusion Criteria not Met	xxx (xxx.x)
Number of Patients not Meeting NPRS of ≥ 4	xxx (xxx.x)
Number of Patients not Meeting Other Inclusion Criteria	xxx (xxx.x)
Number of Patients with Exclusion Criteria Met	xxx (xxx.x)
Missing	xxx (xxx.x)

Note: Percentages based on the total number of enrolled patients.
Patients may fail screening for more than one reason.

Table 14.1.3
Summary of Reasons for Receiving Oliceridine
(Safety Analysis Set)

Initial Setting Specialty ICD-10 Category	Oliceridine <= 4 mg N=XXX n (%)	Oliceridine >4 to 8 mg N=XXX n (%)	Oliceridine >8 to 16 mg N=XXX n (%)	Oliceridine >16 to 36 mg N=XXX n (%)	Oliceridine >36 mg N=XXX n (%)	All Treated Patients N=XXX n (%)
Surgical	xxx (xxxx.x)	xxx (xxxx.x)	xxx (xxxx.x)	xxx (xxxx.x)	xxx (xxxx.x)	xxx (xxxx.x)
<Specialty 1>	xxx (xxxx.x)	xxx (xxxx.x)	xxx (xxxx.x)	xxx (xxxx.x)	xxx (xxxx.x)	xxx (xxxx.x)
<ICD-10 Category>	xxx (xxxx.x)	xxx (xxxx.x)	xxx (xxxx.x)	xxx (xxxx.x)	xxx (xxxx.x)	xxx (xxxx.x)
...	xxx (xxxx.x)	xxx (xxxx.x)	xxx (xxxx.x)	xxx (xxxx.x)	xxx (xxxx.x)	xxx (xxxx.x)
<Specialty 2>	xxx (xxxx.x)	xxx (xxxx.x)	xxx (xxxx.x)	xxx (xxxx.x)	xxx (xxxx.x)	xxx (xxxx.x)
...	xxx (xxxx.x)	xxx (xxxx.x)	xxx (xxxx.x)	xxx (xxxx.x)	xxx (xxxx.x)	xxx (xxxx.x)
Medical	xxx (xxxx.x)	xxx (xxxx.x)	xxx (xxxx.x)	xxx (xxxx.x)	xxx (xxxx.x)	xxx (xxxx.x)
<Specialty 1>	xxx (xxxx.x)	xxx (xxxx.x)	xxx (xxxx.x)	xxx (xxxx.x)	xxx (xxxx.x)	xxx (xxxx.x)
<ICD-10 Category>	xxx (xxxx.x)	xxx (xxxx.x)	xxx (xxxx.x)	xxx (xxxx.x)	xxx (xxxx.x)	xxx (xxxx.x)
...	xxx (xxxx.x)	xxx (xxxx.x)	xxx (xxxx.x)	xxx (xxxx.x)	xxx (xxxx.x)	xxx (xxxx.x)
<Specialty 2>	xxx (xxxx.x)	xxx (xxxx.x)	xxx (xxxx.x)	xxx (xxxx.x)	xxx (xxxx.x)	xxx (xxxx.x)
...	xxx (xxxx.x)	xxx (xxxx.x)	xxx (xxxx.x)	xxx (xxxx.x)	xxx (xxxx.x)	xxx (xxxx.x)
ED	xxx (xxxx.x)	xxx (xxxx.x)	xxx (xxxx.x)	xxx (xxxx.x)	xxx (xxxx.x)	xxx (xxxx.x)
<Specialty 1>	xxx (xxxx.x)	xxx (xxxx.x)	xxx (xxxx.x)	xxx (xxxx.x)	xxx (xxxx.x)	xxx (xxxx.x)
<ICD-10 Category>	xxx (xxxx.x)	xxx (xxxx.x)	xxx (xxxx.x)	xxx (xxxx.x)	xxx (xxxx.x)	xxx (xxxx.x)
...	xxx (xxxx.x)	xxx (xxxx.x)	xxx (xxxx.x)	xxx (xxxx.x)	xxx (xxxx.x)	xxx (xxxx.x)
<Specialty 2>	xxx (xxxx.x)	xxx (xxxx.x)	xxx (xxxx.x)	xxx (xxxx.x)	xxx (xxxx.x)	xxx (xxxx.x)
...	xxx (xxxx.x)	xxx (xxxx.x)	xxx (xxxx.x)	xxx (xxxx.x)	xxx (xxxx.x)	xxx (xxxx.x)

Note: Percentages are based on the number of patients in each cumulative dose group.

Patient are only counted in the category if finding is the reason for patient's participation in the study.

Programmers Note: Sort by initial setting (Surg, Med then ED) and by decreasing frequency(all treated patients column) of ICD-10 category.

Table 14.1.4
Medical History by Body System and Medical Condition
(Safety Analysis Set)

Body System Medical Condition	Oliceridine <= 4 mg N=XXX n (%)	Oliceridine >4 to 8 mg N=XXX n (%)	Oliceridine >8 to 16 mg N=XXX n (%)	Oliceridine >16 to 36 mg N=XXX n (%)	Oliceridine >36 mg N=XXX n (%)	All Treated Patients N=XXX n (%)
Number of Patients with at Least 1 Medical History	xxx (xxx.x)	xxx (xxx.x)	xxx (xxx.x)	xxx (xxx.x)	xxx (xxx.x)	xxx (xxx.x)
<Body System 1>						
<Condition 1>	xxx (xxx.x)	xxx (xxx.x)	xxx (xxx.x)	xxx (xxx.x)	xxx (xxx.x)	xxx (xxx.x)
...	xxx (xxx.x)	xxx (xxx.x)	xxx (xxx.x)	xxx (xxx.x)	xxx (xxx.x)	xxx (xxx.x)
<Condition n>	xxx (xxx.x)	xxx (xxx.x)	xxx (xxx.x)	xxx (xxx.x)	xxx (xxx.x)	xxx (xxx.x)
<Body System 2>						
<Condition 1>	xxx (xxx.x)	xxx (xxx.x)	xxx (xxx.x)	xxx (xxx.x)	xxx (xxx.x)	xxx (xxx.x)
...	xxx (xxx.x)	xxx (xxx.x)	xxx (xxx.x)	xxx (xxx.x)	xxx (xxx.x)	xxx (xxx.x)
<Condition n>	xxx (xxx.x)	xxx (xxx.x)	xxx (xxx.x)	xxx (xxx.x)	xxx (xxx.x)	xxx (xxx.x)
...						

Note: All medical history events were coded using MedDRA version 19.0.

Percentages are based on the number of patients in each cumulative dose group.

Patients are counted once within each body system and condition within each cumulative dose group.

Programmer's Note: Order System Organ Class alphabetically and preferred term alphabetically within each SOC. If SOC wraps to a new page, it should be repeated in each page. Sort UNCODED as first SOC.

Table 14.1.5
Summary of Patient Disposition
(Safety Analysis Set)

Disposition	Oliceridine <= 4 mg N=XXX n (%)	Oliceridine >4 to 8 mg N=XXX n (%)	Oliceridine >8 to 16 mg N=XXX n (%)	Oliceridine >16 to 36 mg N=XXX n (%)	Oliceridine >36 mg N=XXX n (%)	All Treated Patients N=XXX n (%)
Number of Patients That Completed the Study [a]	xxx (xxx.x)	xxx (xxx.x)	xxx (xxx.x)	xxx (xxx.x)	xxx (xxx.x)	xxx (xxx.x)
Number of Patients That Discontinued Early from Study	xxx (xxx.x)	xxx (xxx.x)	xxx (xxx.x)	xxx (xxx.x)	xxx (xxx.x)	xxx (xxx.x)
Reason for Early Discontinuation from Study						
ADVERSE EVENT	xxx (xxx.x)	xxx (xxx.x)	xxx (xxx.x)	xxx (xxx.x)	xxx (xxx.x)	xxx (xxx.x)
LACK OF EFFICACY	xxx (xxx.x)	xxx (xxx.x)	xxx (xxx.x)	xxx (xxx.x)	xxx (xxx.x)	xxx (xxx.x)
LOST TO FOLLOW-UP	xxx (xxx.x)	xxx (xxx.x)	xxx (xxx.x)	xxx (xxx.x)	xxx (xxx.x)	xxx (xxx.x)
. . .	xxx (xxx.x)	xxx (xxx.x)	xxx (xxx.x)	xxx (xxx.x)	xxx (xxx.x)	xxx (xxx.x)
Study Window of Early Discontinuation [b]						
<T30 Minutes>	xxx (xxx.x)	xxx (xxx.x)	xxx (xxx.x)	xxx (xxx.x)	xxx (xxx.x)	xxx (xxx.x)
<T2 Hours>	xxx (xxx.x)	xxx (xxx.x)	xxx (xxx.x)	xxx (xxx.x)	xxx (xxx.x)	xxx (xxx.x)
. . .	xxx (xxx.x)	xxx (xxx.x)	xxx (xxx.x)	xxx (xxx.x)	xxx (xxx.x)	xxx (xxx.x)
<T96 Hours>	xxx (xxx.x)	xxx (xxx.x)	xxx (xxx.x)	xxx (xxx.x)	xxx (xxx.x)	xxx (xxx.x)

Note: Percentages are based on the number of patients in each cumulative dose group.

[a] Because the duration of treatment for each patient in this study will be determined by the clinical need for parenteral opioid therapy, a patient will be considered to be a completer if no early termination reason is indicated.

[b] Study window is defined as the date and time of termination - date and time of the first dose of oliceridine. See section 6.2.3 of the SAP for windowed time point intervals.

Table 14.1.6
Demographic and Baseline Characteristics
(Safety Analysis Set)

Characteristic	Oliceridine <= 4 mg N=XXX	Oliceridine >4 to 8 mg N=XXX	Oliceridine >8 to 16 mg N=XXX	Oliceridine >16 to 36 mg N=XXX	Oliceridine >36 mg N=XXX	All Treated Patients N=XXX
Initial Setting, n(%)						
Surgical	xxx (xxx.x)	xxx (xxx.x)	xxx (xxx.x)	xxx (xxx.x)	xxx (xxx.x)	xxx (xxx.x)
Medical	xxx (xxx.x)	xxx (xxx.x)	xxx (xxx.x)	xxx (xxx.x)	xxx (xxx.x)	xxx (xxx.x)
Emergency Department	xxx (xxx.x)	xxx (xxx.x)	xxx (xxx.x)	xxx (xxx.x)	xxx (xxx.x)	xxx (xxx.x)
Missing	xxx (xxx.x)	xxx (xxx.x)	xxx (xxx.x)	xxx (xxx.x)	xxx (xxx.x)	xxx (xxx.x)
Gender, n(%)						
Male	xxx (xxx.x)	xxx (xxx.x)	xxx (xxx.x)	xxx (xxx.x)	xxx (xxx.x)	xxx (xxx.x)
Female	xxx (xxx.x)	xxx (xxx.x)	xxx (xxx.x)	xxx (xxx.x)	xxx (xxx.x)	xxx (xxx.x)
Missing	xxx (xxx.x)	xxx (xxx.x)	xxx (xxx.x)	xxx (xxx.x)	xxx (xxx.x)	xxx (xxx.x)
Age (Years)						
N	xxx	xxx	xxx	xxx	xxx	xxx
Mean (SD)	xx.x (x.xx)	xx.x (x.xx)	xx.x (x.xx)	xx.x (x.xx)	xx.x (x.xx)	xx.x (x.xx)
Median	xx.x	xx.x	xx.x	xx.x	xx.x	xx.x
Min, Max	xx, xx	xx, xx	xx, xx	xx, xx	xx, xx	xx, xx
Missing	xxx	xxx	xxx	xxx	xxx	xxx
Age Group 1 (Years), n(%)						
< Median	xxx (xxx.x)	xxx (xxx.x)	xxx (xxx.x)	xxx (xxx.x)	xxx (xxx.x)	xxx (xxx.x)
≥ Median	xxx (xxx.x)	xxx (xxx.x)	xxx (xxx.x)	xxx (xxx.x)	xxx (xxx.x)	xxx (xxx.x)
Missing	xxx (xxx.x)	xxx (xxx.x)	xxx (xxx.x)	xxx (xxx.x)	xxx (xxx.x)	xxx (xxx.x)

Note: Percentages are based on the total number of non-missing values in each cumulative dose group.

[a] Extensive Metabolizer = Normal functional levels of CYP2D6 in the liver. Poor Metabolizer = Low functional levels of CYP2D6 in the liver.

Trevena, Inc.
Protocol CP130-3003CONFIDENTIAL
Page x of yTable 14.1.6 (continued)
Demographic and Baseline Characteristics
(Safety Analysis Set)

Characteristic	Oliceridine <= 4 mg N=XXX	Oliceridine >4 to 8 mg N=XXX	Oliceridine >8 to 16 mg N=XXX	Oliceridine >16 to 36 mg N=XXX	Oliceridine >36 mg N=XXX	All Treated Patients N=XXX
Age Group 2 (Years), n(%)						
< 65	xxx (xxx.x)	xxx (xxx.x)	xxx (xxx.x)	xxx (xxx.x)	xxx (xxx.x)	xxx (xxx.x)
>= 65 to < 75	xxx (xxx.x)	xxx (xxx.x)	xxx (xxx.x)	xxx (xxx.x)	xxx (xxx.x)	xxx (xxx.x)
>= 75	xxx (xxx.x)	xxx (xxx.x)	xxx (xxx.x)	xxx (xxx.x)	xxx (xxx.x)	xxx (xxx.x)
Missing	xxx (xxx.x)	xxx (xxx.x)	xxx (xxx.x)	xxx (xxx.x)	xxx (xxx.x)	xxx (xxx.x)
Race, n(%)						
<Race 1>	xxx (xxx.x)	xxx (xxx.x)	xxx (xxx.x)	xxx (xxx.x)	xxx (xxx.x)	xxx (xxx.x)
...	xxx (xxx.x)	xxx (xxx.x)	xxx (xxx.x)	xxx (xxx.x)	xxx (xxx.x)	xxx (xxx.x)
<Race n>	xxx (xxx.x)	xxx (xxx.x)	xxx (xxx.x)	xxx (xxx.x)	xxx (xxx.x)	xxx (xxx.x)
Missing	xxx (xxx.x)	xxx (xxx.x)	xxx (xxx.x)	xxx (xxx.x)	xxx (xxx.x)	xxx (xxx.x)
Race Group, n(%)						
White	xxx (xxx.x)	xxx (xxx.x)	xxx (xxx.x)	xxx (xxx.x)	xxx (xxx.x)	xxx (xxx.x)
Non-White	xxx (xxx.x)	xxx (xxx.x)	xxx (xxx.x)	xxx (xxx.x)	xxx (xxx.x)	xxx (xxx.x)
Missing	xxx (xxx.x)	xxx (xxx.x)	xxx (xxx.x)	xxx (xxx.x)	xxx (xxx.x)	xxx (xxx.x)
Ethnicity, n(%)						
<Ethnicity 1>	xxx (xxx.x)	xxx (xxx.x)	xxx (xxx.x)	xxx (xxx.x)	xxx (xxx.x)	xxx (xxx.x)
...	xxx (xxx.x)	xxx (xxx.x)	xxx (xxx.x)	xxx (xxx.x)	xxx (xxx.x)	xxx (xxx.x)
<Ethnicity n>	xxx (xxx.x)	xxx (xxx.x)	xxx (xxx.x)	xxx (xxx.x)	xxx (xxx.x)	xxx (xxx.x)
Missing	xxx (xxx.x)	xxx (xxx.x)	xxx (xxx.x)	xxx (xxx.x)	xxx (xxx.x)	xxx (xxx.x)
CYP2D6 Metabolizer Status [a], n(%)						
Extensive Metabolizer	xxx (xxx.x)	xxx (xxx.x)	xxx (xxx.x)	xxx (xxx.x)	xxx (xxx.x)	xxx (xxx.x)
Poor Metabolizer	xxx (xxx.x)	xxx (xxx.x)	xxx (xxx.x)	xxx (xxx.x)	xxx (xxx.x)	xxx (xxx.x)
Missing	xxx (xxx.x)	xxx (xxx.x)	xxx (xxx.x)	xxx (xxx.x)	xxx (xxx.x)	xxx (xxx.x)

Note: Percentages are based on the total number of non-missing values in each cumulative dose group.

[a] Extensive Metabolizer = Normal functional levels of CYP2D6 in the liver. Poor Metabolizer = Low functional levels of CYP2D6 in the liver.

Table 14.1.6 (continued)
Demographic and Baseline Characteristics
(Safety Analysis Set)

Characteristic	Oliceridine <= 4 mg N=XXX	Oliceridine >4 to 8 mg N=XXX	Oliceridine >8 to 16 mg N=XXX	Oliceridine >16 to 36 mg N=XXX	Oliceridine >36 mg N=XXX	All Treated Patients N=XXX
Height (cm)						
N	xxx	xxx	xxx	xxx	xxx	xxx
Mean (SD)	xx.x (x.xx)	xx.x (x.xx)	xx.x (x.xx)	xx.x (x.xx)	xx.x (x.xx)	xx.x (x.xx)
Median	xx.x	xx.x	xx.x	xx.x	xx.x	xx.x
Min, Max	xx, xx	xx, xx	xx, xx	xx, xx	xx, xx	xx, xx
Missing	xxx	xxx	xxx	xxx	xxx	xxx
Weight (kg)						
N	xxx	xxx	xxx	xxx	xxx	xxx
Mean (SD)	xx.x (x.xx)	xx.x (x.xx)	xx.x (x.xx)	xx.x (x.xx)	xx.x (x.xx)	xx.x (x.xx)
Median	xx.x	xx.x	xx.x	xx.x	xx.x	xx.x
Min, Max	xx, xx	xx, xx	xx, xx	xx, xx	xx, xx	xx, xx
Missing	xxx	xxx	xxx	xxx	xxx	xxx
BMI (kg/m**2)						
N	xxx	xxx	xxx	xxx	xxx	xxx
Mean (SD)	xx.x (x.xx)	xx.x (x.xx)	xx.x (x.xx)	xx.x (x.xx)	xx.x (x.xx)	xx.x (x.xx)
Median	xx.x	xx.x	xx.x	xx.x	xx.x	xx.x
Min, Max	xx, xx	xx, xx	xx, xx	xx, xx	xx, xx	xx, xx
Missing	xxx	xxx	xxx	xxx	xxx	xxx
BMI Group (kg/m**2), n (%)						
< 25	xxx (xxx.x)	xxx (xxx.x)	xxx (xxx.x)	xxx (xxx.x)	xxx (xxx.x)	xxx (xxx.x)
>= 25	xxx (xxx.x)	xxx (xxx.x)	xxx (xxx.x)	xxx (xxx.x)	xxx (xxx.x)	xxx (xxx.x)
Missing	xxx (xxx.x)	xxx (xxx.x)	xxx (xxx.x)	xxx (xxx.x)	xxx (xxx.x)	xxx (xxx.x)

Note: Percentages are based on the total number of non-missing values in each cumulative dose group.

[a] Extensive Metabolizer = Normal functional levels of CYP2D6 in the liver. Poor Metabolizer = Low functional levels of CYP2D6 in the liver.

Trevena, Inc.
Protocol CP130-3003CONFIDENTIAL
Page x of yTable 14.1.6 (continued)
Demographic and Baseline Characteristics
(Safety Analysis Set)

Characteristic	Oliceridine <= 4 mg N=XXX	Oliceridine >4 to 8 mg N=XXX	Oliceridine >8 to 16 mg N=XXX	Oliceridine >16 to 36 mg N=XXX	Oliceridine >36 mg N=XXX	All Treated Patients N=XXX
Baseline Pain Intensity						
N	xxx	xxx	xxx	xxx	xxx	xxx
Mean (SD)	xx.x (x.xx)	xx.x (x.xx)	xx.x (x.xx)	xx.x (x.xx)	xx.x (x.xx)	xx.x (x.xx)
Median	xx.x	xx.x	xx.x	xx.x	xx.x	xx.x
Min, Max	xx, xx	xx, xx	xx, xx	xx, xx	xx, xx	xx, xx
Missing	xxx	xxx	xxx	xxx	xxx	xxx

Note: Percentages are based on the total number of non-missing values in each cumulative dose group.

[a] Extensive Metabolizer = Normal functional levels of CYP2D6 in the liver. Poor Metabolizer = Low functional levels of CYP2D6 in the liver.

Table 14.1.7
Summary of Prior Medications by Drug Class and Medication
(Safety Analysis Set)

Drug Class Preferred Name [a]	Oliceridine <= 4 mg N=XXX n (%)	Oliceridine >4 to 8 mg N=XXX n (%)	Oliceridine >8 to 16 mg N=XXX n (%)	Oliceridine >16 to 36 mg N=XXX n (%)	Oliceridine >36 mg N=XXX n (%)	All Treated Patients N=XXX n (%)
Number of Patients Receiving a Prior Medication	xxx (xxx.x)	xxx (xxx.x)	xxx (xxx.x)	xxx (xxx.x)	xxx (xxx.x)	xxx (xxx.x)
<Class 1>	xxx (xxx.x)	xxx (xxx.x)	xxx (xxx.x)	xxx (xxx.x)	xxx (xxx.x)	xxx (xxx.x)
<Preferred 1>	xxx (xxx.x)	xxx (xxx.x)	xxx (xxx.x)	xxx (xxx.x)	xxx (xxx.x)	xxx (xxx.x)
...	xxx (xxx.x)	xxx (xxx.x)	xxx (xxx.x)	xxx (xxx.x)	xxx (xxx.x)	xxx (xxx.x)
<Preferred n>	xxx (xxx.x)	xxx (xxx.x)	xxx (xxx.x)	xxx (xxx.x)	xxx (xxx.x)	xxx (xxx.x)
...	xxx (xxx.x)	xxx (xxx.x)	xxx (xxx.x)	xxx (xxx.x)	xxx (xxx.x)	xxx (xxx.x)
...						
<Class n>	xxx (xxx.x)	xxx (xxx.x)	xxx (xxx.x)	xxx (xxx.x)	xxx (xxx.x)	xxx (xxx.x)
<Preferred 1>	xxx (xxx.x)	xxx (xxx.x)	xxx (xxx.x)	xxx (xxx.x)	xxx (xxx.x)	xxx (xxx.x)
...	xxx (xxx.x)	xxx (xxx.x)	xxx (xxx.x)	xxx (xxx.x)	xxx (xxx.x)	xxx (xxx.x)
<Preferred n>	xxx (xxx.x)	xxx (xxx.x)	xxx (xxx.x)	xxx (xxx.x)	xxx (xxx.x)	xxx (xxx.x)
...	xxx (xxx.x)	xxx (xxx.x)	xxx (xxx.x)	xxx (xxx.x)	xxx (xxx.x)	xxx (xxx.x)

Note: Percentages are based on the number of patients in each cumulative dose group.

Patients are counted once within each drug class and preferred name within each cumulative dose group.

[a] All medications were coded using WHO DRUG version Mar 1 2016.

Table 14.1.8
Summary of Concomitant Medications by Drug Class and Medication
(Safety Analysis Set)

Drug Class Preferred Name [a]	Oliceridine =< 4 mg N=XXX n (%)	Oliceridine >4 to 8 mg N=XXX n (%)	Oliceridine >8 to 16 mg N=XXX n (%)	Oliceridine >16 to 36 mg N=XXX n (%)	Oliceridine >36 mg N=XXX n (%)	All Treated Patients N=XXX n (%)
Number of Patients Receiving a Concomitant Medication						
<Class 1>	xxx (xxx.x)	xxx (xxx.x)	xxx (xxx.x)	xxx (xxx.x)	xxx (xxx.x)	xxx (xxx.x)
<Preferred 1>	xxx (xxx.x)	xxx (xxx.x)	xxx (xxx.x)	xxx (xxx.x)	xxx (xxx.x)	xxx (xxx.x)
...	xxx (xxx.x)	xxx (xxx.x)	xxx (xxx.x)	xxx (xxx.x)	xxx (xxx.x)	xxx (xxx.x)
<Preferred n>	xxx (xxx.x)	xxx (xxx.x)	xxx (xxx.x)	xxx (xxx.x)	xxx (xxx.x)	xxx (xxx.x)
...	xxx (xxx.x)	xxx (xxx.x)	xxx (xxx.x)	xxx (xxx.x)	xxx (xxx.x)	xxx (xxx.x)
<Class n>	xxx (xxx.x)	xxx (xxx.x)	xxx (xxx.x)	xxx (xxx.x)	xxx (xxx.x)	xxx (xxx.x)
<Preferred 1>	xxx (xxx.x)	xxx (xxx.x)	xxx (xxx.x)	xxx (xxx.x)	xxx (xxx.x)	xxx (xxx.x)
...	xxx (xxx.x)	xxx (xxx.x)	xxx (xxx.x)	xxx (xxx.x)	xxx (xxx.x)	xxx (xxx.x)
<Preferred n>	xxx (xxx.x)	xxx (xxx.x)	xxx (xxx.x)	xxx (xxx.x)	xxx (xxx.x)	xxx (xxx.x)

Note: Percentages are based on the number of patients in each cumulative dose group.

Patients are counted once within each drug class and preferred name within each cumulative dose group.

[a] All medications were coded using WHO DRUG version Mar 1 2016.

Table 14.2.1
Summary of Numeric Pain Rating Scale Change From Baseline
(Efficacy Analysis Set)

Windowed Time Point [a]	Baseline/ Observed/ Change from Baseline	Oliceridine <= 4 mg N=XXX	Oliceridine >4 to 8 mg N=XXX	Oliceridine >8 to 16 mg N=XXX	Oliceridine >16 to 36 mg N=XXX	Oliceridine >36 mg N=XXX	All Treated Patients N=XXX
Baseline [b]							
N	Observed	xxx xx.x (x.xx)	xxx xx.x (x.xx)	xxx xx.x (x.xx)	xxx xx.x (x.xx)	xxx xx.x (x.xx)	xxx xx.x (x.xx)
Mean (SD)							
Median		xx.x	xx.x	xx.x	xx.x	xx.x	xx.x
Min, Max		xx, xx	xx, xx	xx, xx	xx, xx	xx, xx	xx, xx
Missing		xxx	xxx	xxx	xxx	xxx	xxx
<T30 Minutes>							
N	Baseline[c]	xxx xx.x (x.xx)	xxx xx.x (x.xx)	xxx xx.x (x.xx)	xxx xx.x (x.xx)	xxx xx.x (x.xx)	xxx xx.x (x.xx)
Mean (SD)							
Median		xx.x	xx.x	xx.x	xx.x	xx.x	xx.x
Min, Max		xx, xx	xx, xx	xx, xx	xx, xx	xx, xx	xx, xx
Missing		xxx	xxx	xxx	xxx	xxx	xxx
N	Observed	xxx xx.x (x.xx)	xxx xx.x (x.xx)	xxx xx.x (x.xx)	xxx xx.x (x.xx)	xxx xx.x (x.xx)	xxx xx.x (x.xx)
Mean (SD)							
Median		xx.x	xx.x	xx.x	xx.x	xx.x	xx.x
Min, Max		xx, xx	xx, xx	xx, xx	xx, xx	xx, xx	xx, xx
Missing		xxx	xxx	xxx	xxx	xxx	xxx
N	Change	xxx xx.x (x.xx)	xxx xx.x (x.xx)	xxx xx.x (x.xx)	xxx xx.x (x.xx)	xxx xx.x (x.xx)	xxx xx.x (x.xx)
Mean (SD)							
Median		xx.x	xx.x	xx.x	xx.x	xx.x	xx.x
Min, Max		xx, xx	xx, xx	xx, xx	xx, xx	xx, xx	xx, xx
Missing		xxx	xxx	xxx	xxx	xxx	xxx
...							

[a] See section 6.2.3 of the SAP for windowed time point intervals.

[b] Baseline is the last non-missing value prior to the patient receiving the first dose of oliceridine.

[c] Only patients with both a baseline value and a windowed time point value are summarized at a given windowed time point.

Table 14.3.1.1
Exposure to Study Drug
(Safety Analysis Set)

	Oliceridine <=4 mg N=XXX	Oliceridine >4 to 8 mg N=XXX	Oliceridine >8 to 16 mg N=XXX	Oliceridine >16 to 36 mg N=XXX	Oliceridine > 36 mg N=XXX	All Treated Patients N=XXX
